#### **7.4. Follow-up**

Follow-up visits are scheduled in reference to study vaccination dates as indicated for each visit window.

#### **7.4.1. Visit 02, Day 08, Clinic Visit**

##### **(Window: 7±1 days post first study vaccination)**

- Interim medical history, including an assessment for new medical conditions will be obtained by interview of parent(s)/legal guardian(s) and any changes since the previous clinic visit or contact will be noted.
- Subject's parent(s)/legal guardian(s) will be asked if the subject had any additional blood taken for medical reasons.
- Memory aid information will be reviewed with parent(s)/legal guardian(s).
- All concomitant medications (including solicitation for receipt of any non-study influenza vaccines) will be recorded on the appropriate data collection form prior to the second study vaccination.
- Subject's/parent(s)/legal guardian(s) will be counseled on the avoidance of taking any aspirin or salicylate containing products for 30 days prior to receipt of the first vaccination through 21 days after the last vaccination.
- All AE/AESIs/NOCMCs/SAEs will be recorded on the appropriate data collection form.
- In the event that the subject attends the visit without a parent/legal guardian, the parent/legal guardian will be called to collect updated medical history, concomitant medications, and will be reminded that the subject is to avoid any aspirin or salicylate containing products for 30 days prior to receipt of the first vaccination through 21 days after the last vaccination.
- A limited physical examination to specifically include the nares (including edema), throat, and lungs (including evaluation for wheezing) will be performed and a targeted physical examination may be performed on the other body systems if indicated based on review of interim medical history, by a study clinician licensed to make medical diagnoses and listed on the Form FDA 1572 as the site principal investigator or sub-investigator.
- A nasal swab for sIgA will be obtained.
- Approximately 14 mL of venous blood will be collected for safety labs including WBC, HGB, Platelet Count, ALT, AST, Serum Creatinine, PT and aPTT.
- Approximately 6 mL of venous blood will be collected for serum HAI, HA/NA ELISA and neutralization assays.

- Approximately 16 mL of PBMCs will be collected for IFN- $\gamma$  ELISPOT and CFSE dilution/ICS assays.

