#### **3.2. Study Outcome Measures**

##### **3.2.1. Primary:**

Safety:

- Frequency of solicited upper respiratory and systemic reactogenicity through approximately Day 8 after the first study vaccination.

- 
- Frequency of unsolicited non-serious adverse events from the time of study vaccination through 21 days after the first study vaccination.
  - Frequency of SAEs, regardless of seriousness or relationship to study vaccination, from receipt of the first vaccination throughout the entire study.
  - Frequency of New Onset Chronic Medical Conditions (NOCMC) and AESIs that develop from receipt of vaccination through 3 months after first study vaccination.

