- Approximately 16 mL of PBMCs will be collected for IFN- $\gamma$  ELISPOT and CFSE dilution/ICS assays.
- A urine pregnancy test will be performed on all female adolescent subjects of childbearing potential and must be negative to ensure eligibility.
- Subjects will be enrolled in AdvantageEDCSM and assigned randomly to a treatment arm prior to the first study vaccination.
- Pre-administration reactogenicity assessments will be performed prior to the first study vaccination to establish baseline. Subjects will then receive a single dose of study product or placebo intranasally. Subjects will be observed in the clinic for at least 30 minutes after the first study vaccination. Post-administration reactogenicity assessments will be completed, and any AE/SAEs will be recorded on the appropriate data collection form prior to discharge from the clinic.
- Parent(s)/legal guardian(s) will be provided with a memory aid and other study-related materials to record daily oral temperature, solicited systemic reactions, any unsolicited AEs, and concomitant medications. Parent(s)/legal guardian(s) will be encouraged to take child's oral temperature around the same time each day. Subjects must not eat or drink anything hot or cold, or smoke within 10 minutes prior to taking oral temperature. Parent(s)/legal guardian(s) will be instructed on how to use their memory aid and how to measure and record AEs prior to discharge from the clinic. Parent(s)/legal guardian(s) will be instructed to notify the study center if they develop any severe reactions after the first study vaccination. If the site principal investigator or appropriate sub-investigator deems the reaction severe enough, further instructions will be given to the parent(s)/legal/guardian(s) on the proper course of action, including a return to the clinic for immediate evaluation if appropriate.

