Memory Aids: All parent(s)/legal guardian(s) will complete a subject memory aid from the time of the first study vaccination Day 01 (Visit 01) through 7 days after the first study vaccination. Memory aids will be reviewed with the parent(s)/legal guardian(s) for AEs at the clinic visit following receipt of first study vaccination. If a subject noted ongoing local (nasal or injection site) or systemic reactogenicity on the 7th day following the study vaccination (study Day 8), the memory aid will continue to be reviewed until resolved. The memory aids will not be retained as a source document.

Subjects will be observed in the clinic for at least 30 minutes after each study vaccination. Any AE/SAEs will be recorded on the appropriate data collection form prior to discharge from the clinic.

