#### **11.4.2. Primary Safety Data**

Summaries and analysis of safety data will be presented for the Safety Analysis Population.

Solicited AEs will be summarized by severity for each day after the first study vaccination (Days 1-8 post vaccination) and as the maximum severity over all 8 days. Additionally, solicited AEs will be analyzed by taking the most severe response over the follow-up period, dichotomizing into a binary variable (none versus mild, moderate, or severe) and using standard techniques, such as exact confidence intervals, to summarize the number and percentage of subjects reporting each symptom, any upper respiratory symptom and any systemic symptom by treatment arm.

Unsolicited AEs will be coded by Medical Dictionary for Regulatory Activities (MedDRA®) for preferred term and system organ class (SOC). The number of SAEs, AESIs, and NOCMCs is expected to be small in this trial and will be reported by detailed listing showing the event description, MedDRA preferred term and SOC, relevant dates (study vaccinations and AEs), severity, relatedness, and outcome for each event. If more than 5% of subjects report SAEs, and AESIs, and NOCMCs then the number and percentage of subjects reporting each type of event will be reported by treatment arm and compared using Fisher's Exact test. Unsolicited AEs will be summarized as number and percentage of subjects reporting at least one event in each MedDRA preferred term and SOC, cross tabulated by severity and relationship to study product. Additionally, the proportion of subjects and exact 95% confidence intervals of AEs in aggregate and by MedDRA categories will be computed.

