9.3.1. Solicited Events and Symptoms

Systemic and upper respiratory (local) solicited adverse events were collected pre-vaccination, and systemic and local solicited adverse events were collected 30 minutes post-vaccination and then daily for 7 days after first vaccination and graded on a scale of 0 (absent), 1 (mild), 2 (moderate) and 3 (severe). Systemic events include: fever, feverishness (chills/shivering/sweating), fatigue (tiredness), malaise (general unwell feeling), myalgia (body aches/muscular pain), arthralgia (joint pain), headache, flushing, decreased activity, decreased appetite, abdominal pain, nausea, vomiting, diarrhea, eye pruritus, eye redness (conjunctivitis), and allergy. Local events include: runny nose, stuffy nose/congestion, sneezing, nasal pain/irritation, nasal bleeding/epistaxis, sinus pressure/pain, sore throat/sore/scratchy/itchy or painful throat, cough, trouble breathing/shortness of breath. Wheezing experienced on or before Day 8 is considered a solicited event. The grading scales for solicited systemic and local (upper respiratory) adverse events are provided in [Table 7](#) and [Table 6](#), respectively. Grading for wheezing events is provided in [Table 9](#).

The proportion of subjects reporting at least one solicited adverse event will be summarized for each solicited adverse event, any systemic symptom, any local symptom, and any symptoms. The 95% CI calculated using Blaker methodology from a binomial distribution (SAS Proc Freq with a binomial option) will be presented ([Table 40](#)).

For each systemic and local event, any systemic event, any local event, and any solicited event, the maximum severity over 7 days after first vaccination will be summarized for the Safety population. The number and percentage of subjects reporting each event will be summarized by the maximum severity and study group. For each event the denominator is the number of subjects with non-missing data for the specific event ([Table 42](#)).

The number of subjects reporting a solicited adverse event will be summarized for each day post vaccination in a summary table ([Table 43](#) and [Table 44](#)) and graphically in a bar chart ([Figure 50](#) and [Figure 51](#)). The difference proportion of subjects experiencing any individual symptom, any local or systemic symptom, and any symptom overall will be presented in [Table 41](#).

Solicited adverse events by subject will be presented in [Listing 11](#) and [Listing 12](#).

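### The Visit 02 window lets the only scheduled memory-aid review fall on study Day 7, so the last solicited day (Day 8) can go uncollected

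*Protocol*

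**What the plan says.** The first primary outcome is "Frequency of solicited upper respiratory and systemic reactogenicity through approximately Day 8 after the first study vaccination" (Protocol 3.2.1). Protocol 11.4.2 summarises solicited events by day, "Days 1-8 post vaccination) and as the maximum severity over all 8 days". Protocol 8.1 has parents complete the memory aid from "Day 01 (Visit 01) through 7 days after the first study vaccination", and equates the 7th day after vaccination with study Day 8.

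Visit 02 (Protocol 7.4.1) has "Window: 7±1 days post first study vaccination" and includes review of the aid. In Appendix A this is the only scheduled review. Otherwise the aid is reviewed at an early-termination or unscheduled visit within 8 days of dose 1. Under 8.1, review continues until resolution if a local or systemic reaction is noted as ongoing on study Day 8. The Visit 03 procedures (7.4.2) do not mention the aid.

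Two further statements bear on the aid:

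- **Contents.** Protocol 7.3.1 says parents receive it "to record daily oral temperature, solicited systemic reactions, any unsolicited AEs, and concomitant medications"; upper-respiratory reactions are not named. SAP 9.3.1 says that "systemic and local solicited adverse events were collected 30 minutes post-vaccination and then daily for 7 days after first vaccination".
- **Status.** Protocol 8.1 says "The memory aids will not be retained as a source document", while Protocol Section 12 includes subjects' memory aids in its list of source documents.

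**The concern.** A visit fully within its window can come before the last day that the primary safety analysis covers. The continuation rule in 8.1 does not close the gap, because it is triggered by something noted on Day 8, which a Day 7 visit cannot yet see. No phone call or later review is specified to collect the remaining entry.

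The analysis side is also silent. In SAP 9.3.1 the denominator for maximum severity is the subjects with non-missing data for the event, and SAP 6.5 rules out imputation. Neither says how the maximum is formed when one day is absent. A subject with seven days recorded would apparently stay in the denominator, and a reaction starting on the missing day would read as none. In a study of 50 whose primary objective is safety, this loss is avoidable.

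**Working it through.** **Day count.** Vaccination is Day 1, so k days after dose 1 is study Day k+1.

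- Earliest Visit 02: 7 − 1 = 6 days after dose 1, which is Day 7.
- Latest Visit 02: 7 + 1 = 8 days, which is Day 9.
- End of the solicited period: 7 days after dose 1, which is Day 8.

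So at most one of the eight solicited days falls after the earliest permitted visit. Visits at 7 or 8 days reach or pass Day 8, although a visit during Day 8 does not see that day completed.

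**The plan's own figure.** Protocol Table 3 gives the probability of observing at least one event, 1 − (1 − p)^n. For p = 10%, n = 25: 1 − 0.9^25 = 92.8% (printed 93). For p = 10%, n = 50: 99.5% (printed >99). For p = 1%: 22.2% and 39.5% (printed 22 and 40). The table is not in dispute; it is the baseline for sizing the gap.

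**Size of the loss.** Let f be the share of subjects seen on Day 7 and h the share of affected subjects whose first onset is on Day 8. The recorded incidence is p × (1 − f × h). The documents give neither f nor h, so both are assumptions. If visit dates spread evenly over Days 7, 8 and 9, f is about 0.33 (50/3, about 17 subjects). If onsets spread evenly over eight days, h = 1/8 = 0.125; h = 0.05 represents onsets concentrated earlier.

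| f | h | True 50% reads as | True 10% reads as | Chance of at least one event, n = 25, true 10% |
|---|---|---|---|---|
| 0 | any | 50.0% | 10.0% | 92.8% |
| 0.33 | 0.05 | 0.5 × (1 − 0.0165) = 49.2% | 9.8% | 92.5% |
| 0.33 | 0.125 | 0.5 × (1 − 0.04125) = 47.9% | 9.6% | 92.0% |
| 1 | 0.125 | 0.5 × (1 − 0.125) = 43.8% | 8.75% | 89.9% |

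If both arms lose the same proportion, the difference in proportions planned for SAP Table 41 shrinks by the same factor: by 1.65% to 4.1% of its size with one third seen early, and by 12.5% in the extreme row. Worsening on Day 8 affects the severity grade but not the incidence, and is not sized here.

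**The case against.** The strongest reply is that very little can be lost. The outcome says approximately Day 8, and the visit is titled Day 08, so most subjects may be seen on or after that day. A reaction already present on Day 7 is recorded at Visit 02. The by-day shells (SAP Tables 43 and 44) carry a Not Reported row, so a missing day is visible there. Visit 03 takes an interim history and records all AEs. All of this stands, and it is why the effect is put as small. It does not close the gap: the Visit 03 recording is by recall about two weeks later, with no stated use of the aid, and the maximum-severity table has no Not Reported row.

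A reader might infer several stronger conclusions that the documents do not support.

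- *The aid omits upper-respiratory symptoms.* Only the 7.3.1 sentence points that way. Protocol 8.1 speaks of nasal reactions noted by subjects in its memory-aid paragraph, SAP 9.3.1 has local events collected daily, and SAP Listing 12 names the aid as a source for local symptoms. The form itself is not in the documents, so this is an inconsistency and not a proven omission.
- *Day 8 entries cannot be recovered.* Nothing says the aid is surrendered at Visit 02. Section 8.1 provides for later review in some cases, and Section 12 lists the aid as a source document.
- *M2SR reactogenicity is biased downward relative to placebo.* The window and the aid apply to both blinded arms, and no arm-specific loss is shown.
- *The halting rules are compromised.* Parents are told to notify the centre of severe reactions (7.3.1), independently of Visit 02, and AEs are recorded again at Visit 03.

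**Conclusion.** The timing gap is real and follows from the Protocol's own dates: an in-window Visit 02 can precede Day 8, and no step then secures that day's entry. What may be missed is limited to solicited reactions that first occur or worsen on Day 8, in subjects seen early, in both arms.

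With one third seen early and 5% to 12.5% of first onsets on Day 8, a true 50% incidence reads about 48% to 49%. If all were seen early, with onsets evenly spread, it reads 43.8%. These sizes rest entirely on the assumed visit dates and onset pattern. It would go too far to say that the first primary outcome is under-recorded; the documents support only that it may be, slightly. The contents and source-document points are wording conflicts to reconcile.

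**What to change.** 1. Open the Visit 02 window no earlier than 7 days after dose 1, for example 7 to 9 days. Alternatively, keep ±1 and require any solicited entries through the end of Day 8 that are outstanding at Visit 02 to be collected by phone or at Visit 03 and entered in the eCRF. The second option also covers a visit held before Day 8 is over.
2. Protocol 14.8 indicates that enrolment has finished. If data collection is complete, report in the CSR how many subjects per arm lack a Day 8 entry, and state in SAP 9.3.1 that they are not counted as none for that day.
3. Reconcile the 7.3.1 list of memory-aid contents with Protocol 8.1, SAP 9.3.1 and Listing 12, after checking the form that was issued.
4. Reconcile Protocol 8.1 with Section 12 on whether the aid is a source document.

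The cost of item 1 is one fewer early scheduling day, with a slight shift in the timing of the Day 8 blood and nasal samples and matching edits to 7.4.1, Appendix A and SAP Table 2, or else a short call. Items 2 to 4 need only a count and text edits.

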**7.4.2. Visit 03, Day 22, Clinic Visit**  
**(Window: 21 $\pm$ 2 days post first study vaccination)**

- Interim medical history, including an assessment for new medical conditions will be obtained by interview of parent(s)/legal guardian(s) and any changes since the previous clinic visit or contact will be noted.
- Subject or subject's parent(s)/legal guardian(s) will be asked if the subject had any additional blood taken for medical reasons.
- All concomitant medications (including solicitation for receipt of any non-study influenza vaccines) will be recorded on the appropriate data collection form prior to the second study vaccination.
- Subject's/parent(s)/legal guardian(s) will be counseled on the avoidance of taking any aspirin or salicylate containing products for 30 days prior to receipt of the first vaccination through 21 days after the last vaccination. All AE/AESIs/NOCMCs/SAEs will be recorded on the appropriate data collection form.
- In the event that the subject attends the visit without a parent/legal guardian, the parent/legal guardian will be called to collect updated medical history, concomitant medications, and will be reminded that the subject is to avoid any aspirin or salicylate containing products for 30 days prior to receipt of the first vaccination through 21 days after the last vaccination.
- A targeted physical examination may be performed, if indicated based on review of interim medical history, by a study clinician licensed to make medical diagnoses and listed on the Form FDA 1572 as the site principal investigator or sub-investigator.
- A nasal swab for sIgA will be obtained.
- Approximately 6 mL of venous blood will be collected for serum HAI, HA/NA ELISA and neutralization assays.
- Approximately 16 mL of PBMCs will be collected for IFN- $\gamma$  ELISPOT and CFSE dilution/ICS assays.
- Approximately 4 mL of venous blood will be collected if Hgb drops  $\geq 0.5$ g/dL or  $<$  lower limits of normal from screen to Day 8, draw repeat Hgb.

### **7.4.3. Visit 04, Day 57, Clinic Visit (Window: 56±3 days post first study vaccination)**

- Interim medical history, including an assessment for new medical conditions will be obtained by interview of parent(s)/legal guardian(s) and any changes since the previous clinic visit or contact will be noted.
- Subject or subject's parent(s)/legal guardian(s) will be asked if the subject had any additional blood taken for medical reasons.
- AEs limited to AESIs, NOCMCs, and SAEs will be recorded on the appropriate data collection form.
- A targeted physical examination may be performed, if indicated based on review of interim medical history, by a study clinician licensed to make medical diagnoses and listed on the Form FDA 1572 as the site principal investigator or sub-investigator.
- Subject's/parent(s)/legal guardian(s) will be counseled on the avoidance of taking any aspirin or salicylate containing products for 30 days prior to receipt of the first vaccination through 21 days after the last vaccination.
- In the event that the subject attends the visit without a parent/legal guardian, the parent/legal guardian will be called to collect updated medical history, concomitant medications, and will be reminded that the subject is to avoid any aspirin or salicylate containing products for 30 days prior to receipt of the first vaccination through 21 days after the last vaccination.
- A nasal swab for sIgA will be obtained.
- Approximately 6 mL of venous blood will be collected for serum HAI, HA/NA ELISA and neutralization assays.
- Approximately 16 mL of PBMCs will be collected for IFN- $\gamma$  ELISPOT and CFSE dilution/ICS assays.
- Approximately 4 mL of venous blood will be collected if Hgb level at Day 22 has dropped 0.5 g/dL or more from baseline or is < lower limit of normal. If results at Day 57 still meet that criteria ( $\geq 0.5$  g/dL drop from baseline or < lower limit of normal), no further PBMC collection will be done. If results have recovered to within 0.4 g/dL of baseline at Day 57, resume blood collection plan for the rest of the study.

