#### **7.4.4. Visit 05, Day 92, Second Vaccination (Dose 2), Clinic Visit (Window: 91±14 days post first study vaccination)**

- Interim medical history, including an assessment for new medical conditions will be obtained by interview of parent(s)/legal guardian(s) and any changes since the previous clinic visit or contact will be noted.
- Criteria for administering QIV will be reviewed with parent(s)/legal guardian(s).
- Concomitant medications (limited to aspirin or salicylate containing products) will be recorded on the appropriate data collection form.
- All AESIs/NOCMCs/SAEs will be recorded on the appropriate data collection form. Reporting of AEs occurring since previous visit but before 2nd vaccination is limited to AESIs, NOCMCs, and SAEs.
- A targeted physical examination may be performed prior to the second study vaccination, if indicated based on review of interim medical history, by a study clinician licensed to make medical diagnoses and listed on the Form FDA 1572 as the site principal investigator or sub-investigator.
- Subject's/parent(s)/legal guardian(s) will be counseled on the avoidance of taking any aspirin or salicylate containing products for 30 days prior to receipt of the first vaccination through 21 days after the last vaccination.
- Oral temperature will be obtained to ensure eligibility. Subjects must not eat or drink anything hot or cold, or smoke within 10 minutes prior to taking oral temperature.
- A urine pregnancy test will be performed on all female adolescent subjects of childbearing potential and must be negative to ensure eligibility.
- A nasal swab for sIgA will be obtained.
- Approximately 6 mL of venous blood will be collected for serum HAI, HA/NA ELISA and neutralization assays.
- Approximately 16 mL of PBMCs will be collected for IFN- $\gamma$  ELISPOT and CFSE dilution/ICS assays. Note: PBMCs will not be collected if the HgB was consistently low through Day 57.
- Subjects will receive their second vaccination IM in whichever deltoid they prefer.

- Subjects will receive a single dose of study vaccine via IM injection into the deltoid muscle of the preferred arm. The site of injection and time of administration will be recorded on the appropriated data collection form. Subjects will be observed in the clinic for at least 30 minutes after the second study vaccination.

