## 9. ASSESSMENT OF SAFETY

### 9.1 Specification of Safety Parameters

Safety will be assessed by the frequency and severity of:

1. SAEs occurring from the time of the first study vaccination through 12 months after the first vaccination.
2. AESIs (wheezing, otitis media) and NOCMCs occurring from the time of the first study vaccination through 3 months after the first vaccination.
3. Solicited Adverse Events – reactogenicity events occurring from the time of experimental (first) study vaccination through 7 days after the first study vaccination. See tables listed in [section 9.2.2 and 9.2.6](#) for local upper respiratory, respiratory tract assessment, and systemic symptoms:
4. Unsolicited Non-Serious Adverse Events –non-serious AEs occurring from the time of the first study vaccination through approximately 21 days after the first study vaccination.
5. Clinical safety laboratory AEs occurring at approximately 7 days after the first vaccination. Parameters to be evaluated include a WBC, HGB, Platelet Count, ALT, AST, Serum Creatinine, Ferritin level, PT and aPTT. HGB will also be repeated at Day 22 if there is a drop in HGB level from screen to Day 8 of  $\geq 0.5$  g/dL or results are  $<$  lower limits of normal. If unable to collect at Day 22, collect at Day 57. If drawn at Day 22 and the results are still low, repeat at Day 57. If HGB results are still low at Day 57, no further PBMC collection will be done. HGB and Ferritin level will be drawn at Day 113. If the ferritin is  $< 15$  ng/mL and/or the HGB is less than the lower limits of normal, will recommend follow-up with primary care provider for consideration of multivitamins with iron.

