PBMC (IFN- $\gamma$ ELISPOT and CFSE Dilution/ICS Assays)		X	X	X	X	X 	X 			X 	
Enrollment in AdvantageEDC SM and Randomization		X									
Pre-Administration Reactogenicity		X				X					

Study Visit Number	V00	V01	V02	V03	V04	V05	V06	V07	V08	Early Term	Unscheduled
Study Day post first study vaccination	Screen -28 to -1	Dose 1* D1	D8 ±1	D22 ±2	D57 ±3	Dose 2* D92 ±14	D 113	D 240	D 366		
Study Day post second study vaccination						D1	D22 ±2	D149 ±14	D275 ±14		
Study Vaccination		X				X					
30-minute Evaluation After Study Vaccination		X				X					
Distribute Memory Aid and Study-Related Materials		X									
Review Memory Aid			X							X@	X@
AE Assessment		X	X	X						X#	X#
AESI + NOCMC Assessment			X	X	X	X				X'	X'
SAE Assessment		X	X	X	X	X	X	X	X	X	X
Phone Call								X	X		

- { } Targeted physical examination if indicated based on review of complete or interim medical history
- ^ Will be performed on all female adolescents of childbearing potential at screening and within 24 hours prior to each study vaccination and results must be negative and known prior to each study vaccination.
- # If within 21 days post first study vaccination.
- \* On dose dates, samples must be collected pre-dose
- @ If within 8 days after 1st vaccination
-  If within 3 months post first study vaccination
-  Subject's parent(s)/legal guardian(s) will be asked if the subject had any additional blood taken for medical reasons.  
subject's blood taken for medical reasons
-  Concomitant medications will be limited to collecting aspirin and salicylate containing products
-  Aspirin or salicylate containing products will be collected if within 30 days of the first vaccination through 21 days after the last vaccination
-  Hemoglobin only
-  Collect at Day 22 if Hgb results from screen to Day 8 drop  $\geq 0.5$  g/dL or < lower limits of normal
-  If Hgb is not collected at Day 22 or low at Day 22, collect at Day 57
-  Will not collect PBMCs if Day 57 HgB is low

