4.3. Selection of Study Population

The study population for this clinical trial is 50 male and non-pregnant female children and adolescents between the ages of 9 and 17 who are in good health and meet all eligibility criteria. Specific eligibility criteria can be found in the protocol sections 5.1 (Subject Inclusion Criteria) and 5.2 (Subject Exclusion Criteria). The subjects are recruited from the general population at the participating Vaccine Trial and Evaluation Unit (VTEU) site, Saint Louis University (SLU), which has substantial experience conducting influenza vaccine studies.

Following review of laboratory results for subjects enrolled through August 2018, it was identified that a significant portion had a drop in hemoglobin during the study. The protocol was amended to include screening for pre-existing iron deficiency anemia with ferritin and requiring both normal ferritin and HgB results for enrollment, to reduce the amount of blood collected overall, and to add a contingency regarding specimen collection. Subjects will be monitored after entry in the trial for drops in hemoglobin levels indicating anemia. If HgB levels are consistently low through the visit at approximately Day 57, the subject will no longer have PBMC samples collected at subsequent visits.

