9.6. Clinical Laboratory Evaluations

Clinical laboratory parameters to be evaluated at the Screening Visit (Visit 00) and on Day 08 (Visit 02) will include a White Blood Cell Count (WC), HGB, HCT (only at Visit 00), Platelet Count, ALT, AST, Serum Creatinine, Ferritin (at Visit 00), Prothrombin Time (PT) and Activated Partial Thromboplastin Time (aPTT). The grading scales for clinical laboratory evaluations are presented in Table 11 and Table 10. Clinical laboratory evaluations assessed on Day 1 prior to the first study vaccination will be considered as baseline.

Subjects with HGB below the lower limit of normal (LLN) at Day 8, or subjects who experience a drop of ≥ 0.5 g/dL between screening and Day 8, will have HGB re-drawn at Day 22. If HGB remains low (result is less than LLN or ≥ 0.5 g/dL lower than screening levels) at Day 22, or if HGB is not collected at Day 22, hemoglobin labs will be re-drawn at Day 57. Any subject where HGB results remain low at Day 57 will have no further PBMC collected. HGB and Ferritin will be drawn for all subjects at Day 113 (approximately 22 days post QIV vaccination). Ferritin results taken at Day 57 will be used for clinical decision making only – values will not be graded or included in summaries of clinical laboratory data, but will be included in the listings of hematology results (Listing 15).

The distribution of laboratory results by severity, study day and treatment group will be presented beginning with [Table 54](#), and continuing through [Table 65](#). Descriptive statistics including mean, standard deviation, median, minimum and maximum values and change from baseline by study day will be summarized for each parameter in [Table 59](#) and [Table 67](#). Box plots illustrating the change from baseline for each laboratory parameter will be presented in [Figure 56](#), [Figure 57](#), [Figure 58](#), [Figure 59](#), [Figure 60](#), [Figure 61](#), [Figure 62](#), and [Figure 63](#). Subject visits with abnormal laboratory results, Grade 1 severity or higher, will be presented in [Table 52](#) and [Table 53](#) for chemistry and hematology parameters, respectively. Abnormal results will be summarized by visit and study arm in [Table 58](#) and [Table 66](#) for chemistry and hematology parameters, respectively.

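### Protocol 7.4.3 says both stop and resume for a child whose Day 57 HGB is below the lower limit of normal but within 0.4 g/dL of baseline

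*Protocol*

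**What the plan says.** Protocol 7.4.3 (Visit 04, Day 57) carries two adjacent sentences on what follows a repeat HGB.

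- **Stop.** If Day 57 HGB is still at least 0.5 g/dL under baseline, or is under LLN, then "no further PBMC collection will be done". Either condition is enough.
- **Resume.** "If results have recovered to within 0.4 g/dL of baseline at Day 57, resume blood collection plan for the rest of the study". The only test is the distance from baseline.

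The rule is restated elsewhere, each time as a stop rule without a resume exception:

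- Protocol 7.4.4 (Visit 05), repeated in 7.4.5 and 7.6: "PBMCs will not be collected if the HgB was consistently low through Day 57".
- Protocol 9.1: "If HGB results are still low at Day 57, no further PBMC collection will be done".
- Protocol Appendix A, footnote 7: "Will not collect PBMCs if Day 57 HgB is low".
- SAP 4.3: "If HgB levels are consistently low through the visit at approximately Day 57, the subject will no longer have PBMC samples collected at subsequent visits".
- SAP 9.6: "Any subject where HGB results remain low at Day 57 will have no further PBMC collected". This section also defines low, and the first limb of its definition is "result is less than LLN"; the second is a fall of at least 0.5 g/dL from screening.

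**The concern.** The stop sentence has two limbs joined by *or*, while the resume sentence reverses only one of them. A child who entered close to LLN can come back to within 0.4 g/dL of baseline and still be under LLN. For that child the two sentences give opposite instructions, and whichever one staff follow, they depart from the other. Protocol 15.6 counts any noncompliance with the protocol as a deviation, so the child's handling could be classified either way.

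The rule is a pediatric safeguard. SAP 4.3 and SAP 12 say it was introduced after HGB falls were seen in the children enrolled in 2018. At stake are the PBMC draws at Visits 05 and 06, taken from a child whose HGB is below normal.

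**Working it through.** The plan gives no figure of its own to reproduce. The check asks which HGB values satisfy both sentences.

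**Inputs**

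- Baseline *b* is at least 11.5 g/dL (Protocol 5.1, inclusion 12) and within normal limits (Protocol 8.2.1), so *b* ≥ max(11.5, LLN).
- Stop: *b* − *d* ≥ 0.5 or *d* < LLN, where *d* is Day 57 HGB (Protocol 7.4.3).
- Resume: *b* − *d* ≤ 0.4 (Protocol 7.4.3).
- Assumption: HGB is reported to 0.1 g/dL.
- LLN: no value is given. The SAP table footnotes say only that it depends on age and sex. The grading table in Protocol 9.2.5 is adapted to local ranges and starts Grade 1 at 10.4 or 10.9 g/dL, but those are grading limits and do not fix LLN.

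**Where both sentences apply**

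Both hold when *b* − 0.4 ≤ *d* ≤ LLN − 0.1. This requires *b* ≤ LLN + 0.3. Since *b* ≥ 11.5, it also requires LLN ≥ 11.2. If LLN is 11.1 or lower, a child within 0.4 g/dL of baseline has *d* ≥ 11.5 − 0.4 = 11.1 and cannot be under LLN.

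**Count of (baseline, Day 57) pairs meeting both sentences**

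| Assumed LLN (g/dL) | Baselines involved | Pairs |
|---|---|---|
| ≤ 11.1 | none | 0 |
| 11.2 | 11.5 | 1 |
| 11.3 | 11.5–11.6 | 2 + 1 = 3 |
| 11.4 | 11.5–11.7 | 3 + 2 + 1 = 6 |
| ≥ 11.5 | LLN to LLN + 0.3 | 4 + 3 + 2 + 1 = 10 |

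These are grid values that mark where the wording conflicts. They are not frequencies in children. At 0.1 g/dL no pair is left without an instruction.

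**Example (LLN of 11.5 assumed).** Baseline is 11.6 and Day 22 is 11.0. The fall of 0.6 triggers the Day 57 repeat. Day 57 is 11.3. The fall is now 11.6 − 11.3 = 0.3, so the resume sentence applies; 11.3 < 11.5, so the stop sentence applies too.

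**Blood volume (Protocol Table 2)**

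- PBMC at Visits 05 and 06: 2 × 16 = 32 mL, out of 22 + 30 = 52 mL planned.
- At the 34 kg entry minimum: 32 / 34 = 0.94 mL/kg.
- All draws from Visit 04 to Visit 06: 26 + 22 + 30 = 78 mL, or 78 / 34 = 2.3 mL/kg. The eight-week cap is 9.5 mL/kg, or 9.5 × 34 = 323 mL.

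**With the LLN clause added to the resume sentence**

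Resume becomes *b* − *d* ≤ 0.4 and *d* ≥ LLN. At 0.1 g/dL this is the exact complement of stop, so no pair meets both sentences and none meets neither.

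**The case against.** The strongest reply is that the text already resolves itself. The resume sentence covers results that have recovered, and a child still under LLN is most naturally read as not recovered. It returns the child to a collection plan, and that plan has its own PBMC exclusion at Visits 05 and 06 and at early termination. Every other statement of the rule says stop. Moreover, the conflict needs an LLN above 11.1 g/dL, which the documents do not establish.

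Most of this stands, and it rules out two stronger readings.

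- A reader might infer that the resume sentence cancels the LLN limb. It does not: the two sentences conflict, and the weight of the other text favors stopping.
- A reader might infer that children at this site were bled against the rule, or try to forecast how many. The documents give neither LLN nor any HGB distribution, so a forecast would rest wholly on assumed inputs.

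The reply does not remove the defect. Section 7.4.3 is the instruction staff use at Day 57 and the only place with a resume rule. The later visit notes turn on HGB having been consistently low, a phrase the protocol does not define. Staff who have recorded a child as recovered under 7.4.3 could reasonably decide that the note does not apply.

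**Conclusion.** The contradiction is real and visible on the face of Protocol 7.4.3. The resume sentence is the one to correct, since 9.1, Appendix A footnote 7, the Visit 05 and 06 notes and SAP 9.6 all support stopping.

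The size is small. At most 32 mL of blood per affected child is at issue, probably for no child or very few, and the volume cap is not approached. No endpoint, sample size or error rate is affected; the only samples in question are PBMCs at Days 92 and 113 from any such child. HGB and ferritin are rechecked at Day 113.

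The conclusion assumes reporting to 0.1 g/dL and the current entry criteria. Whether any case can occur depends on an LLN above 11.1 g/dL. The requirement that HGB be within normal limits as well as at least 11.5 g/dL would be redundant if LLN never exceeded 11.5, which hints at a higher LLN for some children but does not prove it. Protocol 14.8 refers to the time after all subjects had enrolled, so the correction matters only for children not yet past Visit 06, for classifying deviations, and for any later protocol that reuses the rule.

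**What to change.** In the resume sentence of Protocol 7.4.3, insert *and are not below the lower limit of normal* directly after the words about being within 0.4 g/dL of baseline, and leave the rest unchanged. The cost is one clause, with no change to design, sample size or analysis.

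The edit brings 7.4.3 into line with the other stop rules but does not harmonize every HGB criterion. SAP 4.5.2 and the footnotes to SAP Tables 60, 61, 66 and 67 trigger a redraw at a fall of more than 0.5 g/dL, whereas Protocol 7.4.3 and SAP 9.6 use at least 0.5 g/dL. That mismatch needs its own correction.
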